5.2 CONSENTING PARTICIPANTS

It is recognised that patients may lack capacity at the time of ICU discharge, and during the days following discharge as a result of their acute illness. Reasons include delirium, severe fatigue, and cognitive impairment (that can especially impact short-term memory and the ability to retain information).

It is important to consider inclusion of all eligible patients, including those who may lack capacity, because patients lacking capacity may benefit from the trial intervention and might respond differently to those who have capacity at this time. Published studies also suggest that around 15% of patients may be delirious at the time of ICU discharge, which is likely to impair mental capacity.²

Eligibility can be confirmed, and patients and/or surrogate decision makers approached, by any individual delegated to do so by the local PI, including doctors, nurses, or other healthcare professionals with appropriate training in study procedures.

Wherever possible, patients should be approached when they are considered to have mental capacity. However, when the clinical and/or research teams consider that they lack mental capacity approaches appropriate to the local legal arrangements for Adults with Incapacity (AWI) should be used.

The timing is at the discretion of the research teams in consultation with clinical teams.

5.2.1 Patients with Mental Capacity

If the clinical team (ICU and/or ward based clinical team) agree for the patient to be approached, the clinical or research team will provide the patient with a Participant Information Leaflet (PIL). They may also provide access to a video describing the trial and what is involved, which can be used by the patient and their relatives to help understand the study. If the patient agrees a member of the research team will introduce and discuss the study. Patients will be allowed to consider participation during any part of the eligibility period, but will need to provide consent within 7 days of ICU discharge.

Where a patient agrees, the patient will be provided with a copy of the consent form, a copy of the form will be filed in the patient's medical notes and a copy filed in the ISF. The informed consent process must be documented in the patient's medical records.

5.2.2 Patients lacking Mental Capacity

5.2.2.1 In England, Wales, and Northern Ireland

An opinion/advice will be obtained in line with the legal requirements for obtaining advice in patients without capacity in England and Wales (Mental Capacity Act 2005). Northern Ireland follows common law; for the purposes of the trial, processes used in England and Wales will be used in Northern Ireland.

The researcher will seek from the opinion of a Personal Consultee (who may be a relative, partner or friend of the participant). This should normally take place during a face-to-face meeting. An authorised staff member/researcher will describe the trial to the individual, and provide them with a PIL and Personal Consultee Declaration (England/Wales and Northern Ireland). They may also provide access to a video describing the trial and what is involved, which can be used by the Personal Consultee to help understand the study. The researcher will seek their opinion about whether the patient should take part in the study. They will be asked to consider what the wishes and feelings of the patient would be if they had capacity. After the researcher has checked that the information sheet is understood, the researcher will invite the Personal Consultee to sign the form and will then countersign it. The Personal Consultee will be provided with a copy of the consent form, a copy of the form will be filed in the patient's medical notes and a copy filed in the ISF.

It is expected that in most cases of incapacity, the opinion of the Personal Consultee will be sought during a face-to-face meeting. When this is not possible, it will be allowed to discuss the study by telephone or other real-time communication media.

For patients who lack capacity, and for whom there is no personal consultee available from who to seek advice during the recruitment window, it will be possible to consult a Professional Consultee. The Professional Consultee will be a nominated individual who has relevant knowledge of the trial and the clinical area, and is not a member of the research team. If the Professional Consultee agrees, they will sign a Professional Consultee declaration form. A copy of the form will be filed in the patient's medical notes and a copy filed in the ISF.

The process must be documented in the patient's medical records.

5.2.2.2 In Scotland

Consent will be obtained in Scotland according to the Adults With Incapacity (Scotland) Act 2000).

The researcher will seek consent from a Nearest Relative/Guardian or Welfare Attorney (who may be a relative, partner or friend of the participant). This will usually take place during a face-to-face meeting. An authorised staff member/researcher will describe the trial to the individual, and provide them with a PIL and Consent Form for Nearest Relative/Guardian or Welfare Attorney (Scotland). They may also provide access to a video describing the trial and what is involved, which can be used by the Nearest Relative/Guardian or Welfare Attorney to help understand the study. The researcher will seek their views about whether the patient should take part in the study. They will be asked to give their consent based on their opinion of the wishes and feelings of the patient if they had capacity. After the researcher has checked that the information sheet is understood, the researcher will invite the Nearest Relative/Guardian or Welfare Attorney to sign the form and will then countersign it. The Nearest Relative/ Guardian or Welfare Attorney will be provided with a copy of the consent form, a copy of the form will be filed in the patient's medical notes and a copy filed in the ISF.

It is expected that in most cases of incapacity, the opinion of the Nearest Relative/Guardian or Welfare Attorney will be sought during a face-to-face meeting. When this is not possible, it will be allowed to discuss the study by telephone or other real-time communication media.

The process for obtaining consent must be documented in the patient's medical records.

5.2.2.3 Procedure once patients regain capacity

Once the participant has recovered from the condition causing incapacity, they will be approached by a member of the research team to obtain permission to continue in the study. The consent to continue process will include: assessment and documentation of capacity; providing the PIL and Consent Form for Participant with Recovered Capacity; allowing sufficient time for the patient to understand the material and ask questions; and, obtaining written informed consent. If the patient agrees to continue in the study they will be asked to sign the form which will then be counter signed by a member of the research team. The patient will be provided with a copy of the consent form, a copy of the form will be filed in the patient's medical notes and a copy filed in the ISF. The informed consent to continue process must be documented in the patient's medical records.

If the participant declines on-going participation in the study the procedures for withdrawal (below) will be followed. In the rare event that the patient does not regain capacity or staff have been unable to obtain consent to continue, the consent/opinion from the Personal Consultee or Nearest Relative/ Guardian or Welfare Attorney or Professional Consultee will continue.

5.2.3 Withdrawal of Study Participants

There will be no pre-defined participant withdrawal criteria based on medical criteria. Participants are free to withdraw from the study at any point or a participant can be withdrawn by the Investigator if this is considered clinically appropriate. In the case of incapacity, the representative of the participant can also withdraw the patient from the trial.

It is recognised that responsible clinicians may decide to suspend group allocation in certain circumstances based on their clinical judgement. Examples may include bleeding events, acute cardiovascular events, or other periods of clinical deterioration. In this situation, the patient should not be withdrawn from the trial unless the clinician specifically requests this. Ideally, the patient should be re-established on group allocation after the acute situation has resolved. Wherever possible the patient should remain in the trial for follow-up even if a decision is made to permanently suspend group allocation (see option 1 below).

If withdrawal occurs, the participant will have the following withdrawal options:

- 1. From any further study intervention only (ie the two transfusion groups). Further blood transfusions at the discretion of the clinical team. However, all follow up data collection (including the visit at 30 days if appropriate) will be completed as far as possible. The priority in this situation is the completion of the primary outcome (SF-36 PCS at 90 days).
- 2. From any further study intervention and data collection. All data collected until the point of withdrawal can be retained. In this situation, effort should be made to request that the primary outcome data at 90 days (SF-36 PCS) can be collected even if other

follow up is not completed. If the participant agrees, then this is re-classified as 'option 1' but restricted to primary outcome.

3. From all aspects of the trial and follow up. All research data collected to be removed from analysis.

If withdrawal occurs, the primary reason for withdrawal will be documented in the participant's case report form, if possible. The type of follow-up (if any) will be documented in the case report form.

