2.3.2 Secondary Endpoints/Outcomes

Patient centred outcomes:

- 1. Physical Component Score (PCS) of the SF-36 HRQoL questionnaire (and its four sub-domains) at 30 and 90 days post-randomisation.
- 2. Patient fatigue (Fatigue Severity Scale (FSS)) at 30, 90 and 180 days post-randomisation
- 3. Mental component score SF-36 (and its four sub-domains) at 30, 90 and 180 days post-randomisation.
- 4. Activities of Daily Living (ADLs) (WHODAS questionnaire⁴) at 90 days post-randomisation
- 5. Patients alive at 30, 90 and 180 days post-randomisation
- 6. Patients alive at 5 years post-randomisation derived from data linkage
- 7. Haemoglobin concentration at 30 days post-randomisation

Resource use and cost-effectiveness (based on data linkage and questionnaires):

- 8. Post-ICU length of hospital stay;
- 9. Care costs during 180 days post-randomisation.

- 10. Incremental cost per QALY at 180 days
- 11. Care costs derived from data linkage during 5 years post-randomisation (depending on results from shorter term outcome analysis)

Process and Safety outcomes:

- 12. Protocol compliance (during intervention index hospital stay)
- 13. Hb concentration (during index hospital stay)
- 14. RBC use (during 90 days follow up)
- 15. New Infections (during 90 days follow-up)
- 16. Transfusion-related adverse events (during 90 days follow-up)
- 17. Major adverse cardiovascular events (MACE; during 90 days follow-up)

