- 2. **Postal** questionnaires will be posted out to participants for completion and return in provided envelope.
- 3. **Online** can be answered directly onto the trial database via a link provided by the central research team.

180 days follow up (+/- 14 days)

- Vital status* will be checked and confirmed by the local research team.
- Follow up questionnaires completion will be undertaken by the local research team.
 - ➤ Completion order as follows to ensure primary endpoint is reached wherever possible:
 - 1. Physical Component Score (PCS) of the SF-36
 - 2. Mental Component Score (MCS) of the SF-36
 - 3. Fatigue Severity Scale (FSS)
 - 4. Health Service Utilisation
- Make telephone contact with the participant at the start of the visit window to alert them to the follow up and confirm the method. Wherever possible complete follow up questionnaires at this call.

Participants will be offered several ways in which to complete and return the follow up questionnaires:

- 1. **Telephone call** the participant can complete with the aid of a member of the trial team. *This is the preferred method.*
- 2. **Postal** questionnaires will be posted out to participants for completion and return in provided envelope.
- 3. **Online** can be answered directly onto the trial database via a link provided by the central research team.

For postal and online follow-up the research team should check whether this has been completed after 7 days and attempt to prompt completion whenever possible.

Follow up with the participant will occur within a 14 day window however, questionnaires may be returned outwith this window. Questionnaires returned after 14 days will not be classed as a deviation.

Five-year follow up will be completed via data linkage. This will only be undertaken if deemed worthwhile after the main trial analysis.

*At all follow ups, before contact is with the participant is attempted, survival status will be confirmed by the participating site using local health records/systems.

Table 1: Follow-up time points and measurements

	able 1: Follow-up time points and measurements Follow-up time point Measurements Comments		
rollow-up tillle pollit	Measurements	Comments	
30 days post	Physical Component Score (PCS) of the SF-36	Follow-up can be undertaken in	
randomisation (7 prior		any clinic (eg post-ICU follow-up	
or 14 days post visit		clinic; routine follow-up clinic)	

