date) ¹	4. New Infections (defined as any clinically suspected or proven infection occurring after	or	
	randomisation requiring a new course of antibiotics)	In a clinical Research Facility	
(surviving patients)	5. Major Adverse Cardiac Events (MACE), comprising: any confirmed stroke, myocardial	or	
	infarction, or cardiovascular death	In the patients home or current	
	6. Transfusion-related adverse events	residence	
	Haemoglobin concentration	or	
		In a hospital ward	
	2. Blood samples for erythrogenesis and inflammatory markers (for patients providing		
	permission for this and where feasible to collect)	Follow up undertaken by local	
		investigator team	
	Health service utilisation questionnaire		
90 days post	Physical Component Score (PCS) of the SF-36	Follow up by postal questionnaire	
randomisation (±14	2. Mental Component Score (MCS) of the SF-36	followed by telephone consultation	
days)¹		if required	
	4. WHODAS ADLs questionnaire		
(surviving patients)	5. New Infections (defined as any clinically suspected or proven infection occurring after		
	, ,	consulting electronic health record	
	6. Major Adverse Cardiac Events (MACE), comprising: any confirmed stroke, myocardial		
	infarction, or cardiovascular death		
		Follow up undertaken by local	
		investigator team	
	9. Health service utilisation questionnaire		

180 days pos		Follow up by postal questionnaire
randomisation (±14 days) ¹	, ,	followed by telephone consultation if required
uays).	4. Survival	ii required
(surviving patients)		Survival determined by local team consulting electronic health record
		Follow up by local investigator
5 years pos		team Five-year outcomes determined by
randomisation ²	Health care resource and costs (via data linkage)	data linkage without needing to contact patients.

¹ If follow up in person is not possible or feasible, or is declined by the patient, then research teams should make efforts to obtain questionnaire data either by postal questionnaire or via telephone.

² the decision to undertake data linkage will be determined based on the results of the main trial and any effects seen.

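### Withdrawal option 2 ends record-based survival follow-up together with questionnaires and visits, and staff are not told to ask whether it may continue

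*Protocol*

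**What the plan says.** Section 5.2.3 gives three withdrawal options.

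- Option 1 stops the allocated transfusion practice only, and "all follow up data collection (including the visit at 30 days if appropriate) will be completed as far as possible".
- Option 2 is worded "From any further study intervention and data collection. All data collected until the point of withdrawal can be retained". It then adds that "effort should be made to request that the primary outcome data at 90 days (SF-36 PCS) can be collected", and "If the participant agrees, then this is re-classified as 'option 1' but restricted to primary outcome".
- Option 3 ends all participation and removes the research data from analysis.

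The same section has the type of follow-up after withdrawal, if any, documented in the case report form.

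Section 6.2 says where survival comes from. At every follow-up, before contact is attempted, "survival status will be confirmed by the participating site using local health records/systems". The 180-day row of Table 1 repeats this: "Survival determined by local team consulting electronic health record". Five-year outcomes, if pursued, come from "data linkage without needing to contact patients".

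Section 2.3.2 lists "Patients alive at 30, 90 and 180 days post-randomisation" among the secondary outcomes. Section 9.2 intends intention-to-treat for all outcomes, with safety data analysed by treatment received, and a Cox model for mortality.

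**The concern.** Option 2 treats data collection as a single block. It therefore stops the data that ask nothing of the participant (vital status from records, and linkage) on the same footing as visits and questionnaires. The one item it tells staff to recover is a questionnaire, which does need the participant. Somebody who wants no more contact but would not mind a record check is offered no option that says so.

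The re-classification rule adds an ambiguity. A participant who leaves under option 2 but agrees to give the PCS becomes an option 1 case limited to the primary outcome. Section 6.2 still requires a record check of vital status before the 90-day contact. Section 5.2.3 does not say whether that result may be kept and analysed, or whether the 180-day check should happen at all.

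What is at stake is survival. For the fixed-time survival outcomes, an option 2 participant has missing status after withdrawal; in a Cox model the participant is censored there. Either is harmless only if withdrawal is unrelated to prognosis given the covariates. The protocol gives reasons to doubt that. An investigator may withdraw a participant on clinical grounds, and a clinician may request withdrawal in a setting where the examples given are bleeding, acute cardiovascular events and deterioration (section 5.2.3). Participants who regain capacity and decline to continue enter the same procedure (section 5.2.2.3). The trial is unblinded (section 10.4), so withdrawal could also differ by arm. An analysis plan cannot repair this, because it cannot use data that the protocol says to stop collecting.

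**Working it through.** **Step 1. What each option leaves available**

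| | Contact-based data | Vital status from records | Linkage |
|---|---|---|---|
| Option 1 | continues as far as possible | continues | continues |
| Option 2 | stops | stops | stops |
| Option 2, PCS agreed | 90-day PCS only | not stated | not stated |
| Option 3 | stops, data removed | stops, data removed | stops |

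No row combines an end to contact with continued use of records. That gap is established from the text alone.

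**Step 2. Which outcomes have a stated record source**

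- Survival: explicit (section 6.2 and Table 1).
- Five-year outcomes: explicit, by linkage, conditional on the main results.
- MACE, infections and transfusion-related events: not fixed. Section 7.5 names the medical record or study questionnaires, depending on the variable. The record is a plausible source in hospital. After discharge the legible text does not settle it.

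**Step 3. The plan's own figures**

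- Observed mortality (section 9.1): 12/182 = 0.0659, or 6.6%, which the protocol rounds to 7%.
- Evaluable sample: 2 × (1.960 + 1.282)² × 12² / 5² = 121.0 per arm, rounded up to 122, so 244 in total, as stated. This rests on the PCS alone and does not depend on the withdrawal wording.

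**Step 4. Possible size of the loss**

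Expected deaths in all: 346 × 12/182 = 22.8, about 23.

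Unrecorded deaths = 346 × (option 2 share) × 12/182. The protocol does not give the share, so a range is assumed.

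| Assumed option 2 share | Participants (346 × share) | Deaths possibly unrecorded |
|---|---|---|
| 1% | 3.5 | 0.2 |
| 2% | 6.9 | 0.5 |
| 5% | 17.3 | 1.1 |
| 10% | 34.6 | 2.3 |
| 15% | 51.9 | 3.4 |

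At the observed death rate these are upper figures, because they assume no death is recorded before withdrawal. If those who withdraw die at a higher rate than average, the figures rise in proportion; the protocol gives no rate for that group.

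**The case against.** The strongest reply is that option 2 is the participant's own decision to end data collection, and honouring it is not a loss to be engineered away. Option 1 is also looser than it looks. It asks for follow-up only as far as possible, so a participant who merely stops answering questionnaires need not be moved to option 2, and record checks would go on. Whether records may be read after withdrawal also depends on consent wording that is not in the documents at hand. All of this stands, and it limits the point to one thing: staff are not told to put the narrower question to a participant who might say yes.

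Three stronger readings are tempting, and the documents do not support them.

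- A reader might infer that all safety events are lost although they come from records. A record source is explicit only for survival and linkage.
- A reader might infer that re-labelling option 2 cases as option 1 misstates attrition in the CONSORT diagram. Section 5.2.3 has both the reason for withdrawal and the type of follow-up documented where available, so attrition by type can still be reported.
- A reader might infer that a few missing deaths would visibly distort the survival comparison. That requires nearly all the losses to fall in one arm and the withdrawn participants to be counted as survivors. The planned Cox model would instead remove them from the risk set at withdrawal.

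It is also fair that the primary outcome is expressly protected, and that for participants who agree to give the PCS, vital status to about day 90 would be known to the site in practice. Only permission to use it is unclear.

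**Conclusion.** The point holds in a limited form. As written, option 2 stops survival follow-up and linkage that need no contact, asks back only the 90-day PCS, and leaves the use of vital status unclear after re-classification. This bears on listed survival outcomes under an intended intention-to-treat analysis, and the missingness may be related to prognosis.

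The effect is probably small: at most about 0.2 to 3.4 deaths out of roughly 23. That range rests on an assumed option 2 share of 1% to 15%, on applying the observed 12/182 to the full 346, and on withdrawn participants dying at the average rate. No claim is made about the direction of any bias. The change is worth making because it is cheap and deaths are few, not because the trial's main conclusion is threatened.

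**What to change.** Amend option 2 in section 5.2.3 as follows.

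1. Staff ask, as its own yes/no, whether follow-up from records may continue without contact: survival and linkage, plus safety events where the medical record is the source.
2. Agreement to give the 90-day PCS is recorded as a separate yes/no.
3. The text states that vital status is kept and analysed when the participant agrees, including when the PCS is the only questionnaire given.
4. A complete stop to data collection remains for anyone who refuses.

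The cost is an amendment covering section 5.2.3, the withdrawal CRF and the information leaflet. Sites already check records at each follow-up, so little extra work follows. The figures of 244 evaluable and 346 randomised do not change. Participants already withdrawn under option 2 are not recovered unless they agree.
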